The effect of food on LY3526318 PK will be explored in only female participants enrolled in the 100-mg cohort and in the 400-mg cohorts. The initial dose will be administered after an approximately 8-hour fast, followed by a washout period of at least 1 week, and a second dose administration following a standardized high-fat meal. To ensure a sufficient number of females for the food effect assessment at 100-mg dose level, the 100-mg cohort will be expanded to 12 participants (8 females and 4 males). An additional cohort (Cohort 10) will assess the effect of food on LY3526318 PK in 8 female participants. All participants in this cohort will receive 100 mg LY3526318 with standardized high fat meal in an open-label, 3-way crossover manner (meal administered prior to dose, at 30 minutes and at 1 hour post dose).

Except for the second dose in the food effect assessment cohorts, all other doses are planned to be administered after an approximately 8-hour fast. However, following a review of the 100-mg and/or 400-mg fed and fasted data, subsequent cohorts may be administered with food.

Participants will return to the CRU for a final follow-up visit approximately 9 days after study drug administration or after the final fed-state dose for female participants in the 100- and 400-mg cohorts.

Part B - MAD

The multiple-ascending doses of LY3526318 or placebo will be administered, at planned dose levels of 100, 400, and 1000 mg, once daily for 14 days in 3 cohorts of 8 female participants each. It is likely that 1 or more dose levels in Part B may exceed the approximate 10x margin to the projected NOAEL-equivalent exposures for males; for this

reason, only female participants will be enrolled in Part B. The planned dose levels may be updated following a review of safety and PK data from Part A and they will not exceed those studied in Part A.

The first cohort of Part B will be administered LY3526318 following a review of Part A safety and PK data. Dose escalations to subsequent cohorts may occur after review of safety data and available PK data through 14 days from at least 6 participants in the prior cohort.

Following a screening period of up to 28 days, eligible participants will be confined to the CRU from Day -1, until all study assessments are completed on Days 15, 18, and 19 for Cohorts 7, 8, and 9, respectively. Within each cohort, participants will be randomly assigned to receive LY3526318 or placebo in a 6:2 ratio.

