LY3526318 or matching placebo is planned to be administered in an 8-hour fasting state once daily for 14 days. However, following a review of the food effect data from Part A, all doses may be administered with food.

Participants will return to the CRU for a final visit on Day 23.

Number of Participants:

Part A: Approximately 60 participants will be randomized to achieve 8 evaluable participants per cohort (6 LY3526318:2 placebo), except for the 100-mg cohort that will include 8 evaluable females and 4 evaluable males (females: 6 LY3526318:2 placebo; males: 3 LY3526318:1 placebo) and 100-mg food assessment cohort (Cohort 10) that will include 8 evaluable females and all will receive LY3526318 in an open-label manner.

Part B: Approximately 24 participants will be randomized to achieve 8 evaluable participants per cohort (6 LY3526318:2 placebo).

Additional cohorts of up to 8 participants each may be enrolled in either part of the study. Such additional cohorts may be enrolled in case intermediate or additional dose level(s) need to be studied or additional food effect need to be studied at other than planned dose levels.

Statistical Analysis:

Safety: The primary safety endpoints are the numbers of treatment-emergent serious adverse events and adverse events. Summary statistics for each cohort will be provided by dose level and for all placebo participants combined.

Pharmacokinetic Parameters: Plasma PK parameters for LY3526318 and metabolite(s) of interest will be calculated using noncompartmental methods after single- and multiple-dose administration. Pharmacokinetic parameters will be summarized by dose level using descriptive statistics. Mean and individual plasma concentration versus time curves for LY3526318 will be represented graphically.

2 Schedule of Activities

Table 2-1 Study Schedule Protocol J2D-MC-CVAA: Part A Cohorts 1-6 (SAD)

	S	Treatment/ In CRU				Posttreatment	ED^a
Study Day	≤28	-1	1	2	3	10	
Visit Window (days)						±2	
Visits	1^b	2^c				3	
CRU admission		X					
CRU discharge					X		
Participant information (including I/E criteria)	X	X					
Informed consent	X						
Medical history	X						
Height	X						
Weight	X		X			X	X
Physical examination (complete [C] or directed [D])	C	D	D	D	D	C	C
Urine drug screen and ethanol test	X	X					
Vital signs including temperature	X	X	X (predose, 2 h, 4 h, 8 h)	X	X	X	X
Hematology and clinical chemistry	X	X		X ^d	X ^d	X	X
Urinalysis ^e	X	X					
Pregnancy test (serum beta-hCG) ^f	X	X				X	X

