^h Study drug will be administered once daily in the CRU through Day 14, and the exact time of administration will be recorded. All doses are planned to be administered in a fasting state; however, following a review of the food effect data from Part A, all doses may be administered with food. Fasting on PK sampling days is defined as at least 8 hours predose and 4 hours postdose. Fasting on non-PK and predose only PK sampling days is defined as at least 8 hours predose and 2 hours postdose on all other indicated days.

ⁱ On Days 1 and Day 14, PK samples will be collected at time zero (predose) and at approximately at 1, 2, 4, 6, 8, and 12 hours after dosing. On Day 2 (at predose) and on Day 15 (prior to discharge), 1 PK sample will be taken at 24 hours postdose. Predose PK samples will also be obtained on Days 3, 5, and 8. If applicable, a sample will be collected at the ED visit. PK sample collection times are provided as a guidance and may be modified based on clinical needs. Actual dates and times of sample collection must be recorded. The following time intervals are proposed: predose samples may be obtained between waking up and dosing. Postdose samples may be obtained within $\pm 5\%$ of the scheduled collection time. Post-assay remaining PK plasma samples may be stored for metabolite identification.

Table 2-4 **Study Schedule Protocol J2D-MC-CVAA: Part B (MAD)-Cohort 8**

	S	Treatment/In CRU											Post treatment	ED ^a
		-1	1	2	3	5	8	14	15	16	17	18		
Study Day	≤28												23	
Visit Window (days)													±2	
Visits	1^b							2					3	
CRU admission		X												
CRU discharge												X		
Participant information (including I/E criteria)	X	X												
Informed consent	X													
Medical history	X													
Height	X													
Weight	X		X										X	X
Physical examination (complete [C] or directed [D])	C	D	D	D	D	D	D	D	D	D	D		C	C
Urine drug screen and ethanol test	X	X												
Vital signs including temperature ^c	X	X	X	X	X	X	X	X					X	X
Hematology and clinical chemistry ^d	X	X		X			X	X					X	X
Urinalysis ^e	X	X												
Pregnancy test (serum beta-hCG) ^f	X	X											X	X
HIV, HCV, HBsAg	X													
ECG ^g	X		X					X					X	X
C-SSRS	X	X											X	X
Randomization			X											
Study drug administration ^h						X	X							
PK blood sample ⁱ			X	X	X	X	X	X	X	X	X			X
Adverse event									X	X	X			
Concomitant medications									X	X	X			

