Appendix 8. Protocol Amendment: J2D-MC-CVAA(b)

Protocol J2D-MC-CVAA has been amended; the new will be indicated as amendment (b) and will be used to conduct the study in place of any preceding version of the protocol.

The overall changes and rationale for the changes made to this protocol are as follows:

Section	Changes made	Rationale for the change
2. Study Schedule Protocol J2D-MC-CVAA: Part B (MAD) and associated text throughout protocol	Two additional SOE tables for Cohorts 8 and 9 to clearly indicate differing in house stays for additional PK sample collection regimens between the MAD cohorts. For Cohorts 8 and 9, the revised PK sample collection schedule runs through 96 and 120 hours post Day 14 dose, respectively, with only 3 PK samples added in each cohort.	SAD PK data resulted in a longer half-life than was predicted, so additional collections required to characterize the terminal elimination of LY3526318
2. Study Schedule Protocol J2D-MC-CVAA: Part B (MAD)	Temperature timepoints revised to be consistent with Vital Sign timepoints	Administrative update
Appendix 5. Blood Sampling Summary	Revised blood volume based on additional PK samples	Same as above.
7.1 Treatment Administered	Revised the capsule strengths from “10 mg and 100 mg” to “10 mg to 100mg”	Capsules will be prepared at dosage strengths administered.

Revised Protocol Sections

Note: Deletions have been identified by ~~strike-throughs~~ or grayed out for figures. Additions have been identified by the use of underscore.

2 Schedule of Activities

Study Schedule Protocol J2D-MC-CVAA: Part B (MAD)-Cohort 7

	S	Treatment/In CRU								Post treatment	ED ^a
Study Day	≤28	-1	1	2	3	5	8	14	15	23	
Visit Window (days)										±2	
Visits	1 ^b	2								3	
CRU admission		X									
CRU discharge									X		
Participant information (including I/E criteria)	X	X									
Informed consent	X										
Medical history	X										
Height	X										
Weight	X		X							X	X
Physical examination (complete [C] or directed [D])	C	D	D	D	D	D	D	D		C	C
Urine drug screen and ethanol test	X	X									
Vital signs including temperature ^c	X	X	X	X	X	X	X	X		X	X
Hematology and clinical chemistry ^d	X	X		X			X	X		X	X
Urinalysis ^e	X	X									
Pregnancy test (serum beta-hCG) ^f	X	X								X	X
HIV, HCV, HBsAg	X										
ECG ^g	X		X					X		X	X
C-SSRS	X	X							X	X	X
Randomization			X								
Study drug administration ^h					← X →						
PK blood sample ⁱ			X	X	X	X	X	X	X		X
Adverse event					← X →						

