9.1.4 Pooling

Summary statistics will be calculated by treatment (and time point, if applicable). Placebo data will be pooled for Parts A (SAD) and B (MAD). Placebo data from the periods under fed conditions (i.e. Period 2 for Cohorts 3 and 4) will be pooled and reported as separated treatment.

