9.2.2 Treatment/Subject Grouping

In summary tables, data will be presented by study part and treatment.

Table 3 Part, Cohort and Treatment Labels

Label	Grouping
Study Part	Part A (SAD) Part B (MAD)
Cohorts	Part A: 1-6 and 10 Part B: 7-9
Planned Treatments	Part A (SAD): – Placebo – Placebo fed – 10 mg LY – 50 mg LY – 100 mg LY – 30 mg LY fed – 200 mg LY – 200 mg LY fed – 300 mg LY – 100 mg LY fed (-30 min) – 100 mg LY fed (+30 min) – 100 mg LY fed (+60 min) Part B (MAD): – Placebo QD – 30 mg LY QD – 60 mg LY QD – 100 mg LY QD

LY = LY 3526318; QD = once daily

For subjects for which the actual treatment received does not match the planned treatment, the treatment actually received will be used for the analysis, in any summaries or analysis. In case this leads the number of subjects receiving those actual treatments being less than 2, the data for these subjects will only be listed and not included in any summaries or analyses.

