18.1.1 Adverse Events

Treatment-emergent adverse events (TEAE) are those which occur after the first dose of study drug.

All AEs (including non-treatment-emergent events) will be listed, including the AE description (verbatim term), Medical Dictionary for Regulatory Activities (MedDRA) system organ class (SOC) and preferred term (PT), start date and time, end date and time, severity, relation to study drug, seriousness, action taken, and outcome.

All AE summaries will include only TEAE. All TEAEs occurring following dosing will be attributed to the treatment that was received.

A breakdown of the number of TEAEs, and the number and percentage of subjects reporting each TEAE, categorized by system organ class and preferred term coded according to MedDRA (Version 22.1), will be presented by treatment and overall for each study part. One table is presented for all TEAEs and one table is presented for TEAEs considered to be related to the study medication. Subjects will only be counted once within each SOC or PT per treatment.

Additionally, a summary table with TEAEs by severity and relationship to study drug will be presented by study part and treatment.

The following missing data will be imputed as defined (for calculations only / will not be presented):

- Missing AE start and / or end times for the calculation of onset and duration will be assumed to be at 00:01 for a start time and 23:59 for end times
- Missing AE severity or relationship will be assumed to be severe or related, respectively
- Missing AE start times for the determination of treatment emergence will be assumed to occur after treatment unless partial date documents the AE as happening prior to treatment
- Missing AE start times for the determination of treatment assignment will be assumed to occur after treatment on the recorded date
- Missing AE start date will be assumed to be after treatment for the determination of TEAE and on treatment

For the US Clinical Trials Registry (CTR), a CTRAE summary table and the CTRAESUMM SAS dataset will be provided separately from the TFL created for CSR. The table and corresponding dataset will be created according to the specifications provided by the Sponsor.

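### In Part B, in-unit observation after the last dose lengthens with dose, while the SAP tabulates adverse events by dose over one open window; any bias is probably small, and a split by onset would give a like-for-like reading

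*Protocol*

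**What the plan says.** **Length of stay.** The protocol synopsis (Part B) confines participants from Day -1 "until all study assessments are completed on Days 15, 18, and 19 for Cohorts 7, 8, and 9, respectively". Section 5.1 gives the same days. Amendment (b) introduced the difference; Appendix 8 says the new schedule tables were added to "clearly indicate differing in house stays for additional PK sample collection regimens between the MAD cohorts", because the half-life seen in Part A was longer than predicted.

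**Dose order.** The protocol planned "planned dose levels of 100, 400, and 1000 mg, once daily for 14 days in 3 cohorts of 8 female participants each". SAP Section 6.2 gives the doses actually used in Cohorts 7, 8 and 9, and the analysis labels in SAP Section 9.2.2 are "30 mg LY QD – 60 mg LY QD – 100 mg LY QD". In both, dose rises with cohort number.

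**What is the same in every cohort.** "Study drug will be administered once daily in the CRU through Day 14", and "Participants will return to the CRU for a final visit on Day 23" (window ±2 days).

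**Analysis.** SAP Section 18.1.1 counts as treatment-emergent any event after the first dose and sets no end day. "All TEAEs occurring following dosing will be attributed to the treatment that was received". Counts and percentages are shown by treatment, with no split at discharge, no common window and no person-time rate. SAP Section 9.1.4 pools placebo, and Table 3 of the SAP has a single once-daily placebo group for Part B.

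**SAP design text.** SAP Section 6.0 still ends the stay on Day 15 for all of Part B, although the SAP's own Appendix 2 reproduces the longer schedules for Cohorts 8 and 9.

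**The concern.** Adverse events are the primary endpoint of Part B, and the summary by dose is what a reader will look at first. An event that occurs in the unit is more likely to be noticed and recorded than one that occurs at home. If so, the two higher doses have more opportunity to show events after dosing has stopped, for a reason unrelated to the drug.

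Procedures differ as well. As the schedule tables were extracted, Cohort 7 has no directed physical examination between Day 14 and Day 23, Cohort 8 has three, and Cohort 9 has four or five. The extra PK blood draws in Cohorts 8 and 9 all fall after Cohort 7 has gone home, and an event caused by a draw would count as treatment-emergent.

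Each cohort's two placebo participants share its length of stay and so could serve as a control for this. Pooling placebo over the three cohorts removes that matching. The direction of any bias is that of a dose-response.

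**Working it through.** **The plan's own figures.** Part B has 3 × 8 = 24 participants, 18 active and 6 placebo, as stated. The PK sample counts in Appendix 5 also reproduce:
- Cohort 7: 7 (Day 1) + 7 (Day 14) + 2 (Days 2 and 15) + 3 (Days 3, 5, 8) = 19.
- Cohorts 8 and 9: 7 + 7 + 4 (Days 2, 3, 5, 8) + 4 (after the Day 14 dose) = 22.

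The difference is three draws.

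**Days in the unit, counted from Day 1 to Day 23.**

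| Cohort | Dose | In-unit days d | Share of 23 | Days at home | In-unit share of Days 15-23 |
|---|---|---|---|---|---|
| 7 | 30 mg | 15 | 65% | 8 | 1/9 = 11% |
| 8 | 60 mg | 18 | 78% | 5 | 4/9 = 44% |
| 9 | 100 mg | 19 | 83% | 4 | 5/9 = 56% |

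Pooled placebo averages (15 + 18 + 19)/3 = 17.33 in-unit days, or 75% of 23.

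**Model (assumed).** The documents give neither an adverse-event rate nor a detection rate at home. Take a constant true rate over Days 1-23, no drug effect, and in-unit detection r times that at home. The expected recorded count is then proportional to d + (23 − d)/r.

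| r | Cohort 7 | Cohort 9 | Ratio 9:7 |
|---|---|---|---|
| 1 (full capture at home) | 23 | 23 | 1.00 |
| 1.5 | 20.33 | 21.67 | 1.07 |
| 2 | 19 | 21 | 1.11 |
| 3 | 17.67 | 20.33 | 1.15 |
| no capture at home | 15 | 19 | 1.27 |

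With r = 2, a final visit on Day 21 or Day 25 instead of Day 23 leaves the ratio at 20/18 = 1.11 or 22/20 = 1.10.

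**Against pooled placebo.** With no capture at home, the active-to-placebo ratios for Cohorts 7, 8 and 9 are 15/17.33 = 0.87, 18/17.33 = 1.04 and 19/17.33 = 1.10. With r = 2 the placebo mean is (19 + 20.5 + 21)/3 = 20.17, and the ratios are 0.94, 1.02 and 1.04.

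**Size in events.** Assume 0.05 events per person-day, 6 active participants and r = 2. Cohort 7 expects 6 × 0.05 × 19 = 5.70 and Cohort 9 expects 6 × 0.05 × 21 = 6.30, a difference of 0.60. The Poisson standard deviation of that difference is √(5.70 + 6.30) ≈ 3.5. At the extreme considered (0.10 per day, no capture at home) the counts are 9.0 and 11.4, a difference of 2.4 against √20.4 ≈ 4.5.

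**After the change.** From first dose to 24 hours after the Day 14 dose is 14 days, all in the unit for every cohort and its placebo participants. The ratio is 1.00 for any r. At 0.05 per person-day, each cohort of 6 active participants expects 6 × 0.05 × 14 = 4.2 events.

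**The case against.** Most ascertainment is already equal. Dosing days and the final visit are the same. As extracted, no cohort has laboratory tests, vital signs or ECGs between Day 14 and Day 23. Serious events are collected for 30 days after the last dose in all cohorts (Protocol Section 9.2.1). The study is unpowered and the SAP plans no formal testing, so the comparison is a descriptive table in which chance far outweighs the bias. Every event is listed with its start date and time, so a reader could reconstruct the split. All of this stands, and it limits the size of the point. It does not remove an asymmetry that follows dose by design.

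Readers might draw three stronger conclusions that the documents do not support.
- *Dose-escalation decisions were distorted.* They rest on data through 14 days (synopsis) or 15 days (Protocol Section 7.4.1.2), before the stays diverge.
- *Events at home depend on recall at Day 23.* The protocol does not say how they are elicited after discharge. If they are fully reported at that visit, the bias is zero.
- *Pooled placebo is an unfair comparator throughout.* Every cohort is randomized 6:2, so pooled placebo has the same mix of stays as pooled active, and Cohort 8 (78% in the unit) is close to it (75%). The mismatch is mainly at Cohorts 7 and 9.

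Cutting the main analysis at Day 15 is also tempting. The half-life was longer than predicted, so later events may be drug-related, and the protocol's primary endpoint is not truncated. Nor is the end of Day 15 a common in-unit limit, since Cohort 7 is discharged during that day.

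**Conclusion.** The point holds as a modest one. Observation and procedures after the last dose rise with dose in Part B, and the planned table neither separates that period nor keeps the placebo participants matched on length of stay.

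The difference in setting is confined to Days 15-19. With no drug effect, the Cohort 9 to Cohort 7 ratio is 1.00 under full capture at home, about 1.07 to 1.15 if in-unit detection is 1.5 to 3 times that at home, and at most 1.27. These figures rest on an assumed constant event rate and an assumed detection ratio; neither is in the documents. At the assumed 0.05 events per person-day with half capture at home, the effect is 0.6 events between two groups of six.

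A reader might infer that any rise in events from 30 to 100 mg would be an artefact of the stays. The documents do not support that: the ceiling needs no event at home ever to be reported, and a clear rise within the dosing period could not come from this source.

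**What to change.** - Keep the full-window table of treatment-emergent events as the main Part B summary.
- In SAP Section 18.1.1 and Table 14.3.1.1 (MAD part), add a split by onset: first dose to 24 hours after the Day 14 dose, and later. Footnote the discharge day of each cohort.
- State that any like-for-like reading across doses and against pooled placebo rests on the common-window column. The later column is where the imbalance concentrates. Under the same model applied to Days 15-23, the Cohort 9:7 ratio there is [5 + 4/r]/[1 + 8/r], which is 1.21, 1.40 and 1.73 for r = 1.5, 2 and 3.
- Correct SAP Section 6.0 so that the Part B stays read Day 15, 18 and 19 for Cohorts 7, 8 and 9.

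The cost is SAP wording and one filter on onset times that are already collected. The downside is one more column with small counts.
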